5.4 Subject Populations

Three subject populations, Intent to Treat (ITT) population, According to Protocol (ATP) population, and Safety population, will be considered in this study.

ITT Population

The ITT population will include all subjects who have been randomized into the study.

ATP Population

The ATP population is described below by Cohort

Cohort 1 subjects who meet the following criteria will be included in the ATP population:

- Receive investigational product (MEDI-563 or placebo), and
- Have airway mucosal biopsy results at screening and Study Day 28, and
- Do not receive a burst of corticosteroids (oral, injectable, IV) within 28 days prior to the second airway biopsy (Study Day 28)

Cohort 2 subjects who meet the following criteria will be included in the ATP population:

- Receive 3 doses of investigational product (MEDI-563 or placebo), and
- Have airway mucosal biopsy results at screening and Study Day 84, and
- Do not receive a burst of corticosteroids (oral, injectable, IV) within 28 days prior to the second airway biopsy (Study Day 84), and

• Do not contract an upper or lower respiratory infection requiring antibiotics or antivirals within 28 days prior to the second airway biopsy (Study Day 84)

Safety Population

The safety population will include all subjects who receive study drug. All safety analyses will be based on the safety population.

5.5 Primary Endpoints

The primary objectives of this study are to evaluate the safety and tolerability and to evaluate the effects of MEDI-563 on airway mucosal eosinophils 28 days after completion of dosing in adults with asthma. Adverse events will be described by system organ class (SOC), severity, and relationship to study drug through Study Day 84 (Cohort 1) or through Study Day 140 (Cohort 2). Serious adverse events will be described by SOC, severity, and relationship to study drug through Study Day 140 (Cohort 2), or through the end of long-term follow-up, if applicable. As safety assessments, NK cell counts, serum CRP, ECP, EDN, IL-5, IL-6, and tryptase levels, and ECG will be evaluated in the MEDI-563 and placebo groups as changes from baseline. Percent change from baseline in eosinophil counts in the airway mucosa (on Study Day 28 for Cohort 1 or on Study Day 84 for Cohort 2) will be summarized by cohort, treatment group, and visit.

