The primary endpoints of this study are to evaluate the safety and tolerability of MEDI-563 and to evaluate the effect of MEDI-563 on airway mucosal eosinophils 28 days after completion of dosing in adults with asthma. Safety and tolerability will be assessed by summarizing AEs. The occurrence of AEs will be reported from the time the subject signs the informed consent through End of Study/Study Termination (Study Day 84 for Cohort 1 or Study Day 140 for Cohort 2). The occurrence of SAEs will be reported from the time the subject signs the informed consent through End of Study/Study Termination (Study Day 84 for Cohort 1 or Study Day 140 for Cohort 2), or until the long-term follow-up period is complete, if applicable. Other variables used for the safety assessments include serum chemistry, complete blood count (CBC) with differential and platelets, and urinalysis. These variables as well as their changes from baseline will be summarized descriptively. Percent change from baseline in eosinophil counts in the airway mucosa (Study Day 28 for Cohort 1 or Study Day 84 for Cohort 2) will be summarized by cohort and treatment group.

The secondary endpoints of this study are to evaluate the PK and IM of MEDI-563. Noncompartmetal pharmacokinetic parameters to be reported include but are not limited to, the maximum observed plasma concentration of MEDI-563 (C_{max}), area under the concentration-time curve (AUC), the terminal elimination half-life ($t_{1/2}$) and systemic clearance (CL) for Cohort 1, if the data allow. For Cohort 2, C_{max} and pre-dose trough (C_{min}) plasma concentrations will be summarized following each dose. Descriptive statistics of these noncompartmental parameters by dose cohort will also be provided. Immunogenicity will be evaluated by analyzing plasma samples for the detection of the presence of anti-MEDI-563 antibodies following MEDI-563 dosing. Immunogenicity results will be listed for each subject, and the percentage of subjects who developed detectable anti-MEDI-563 antibodies will be calculated and reported.

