1.4 Clinical Experience with MEDI-563

MEDI-563 is being evaluated in 4 clinical studies, including the current study. One study has completed enrollment and data analysis is ongoing (MI-CP158) and the remaining 3 studies are ongoing (MI-CP166, MI-CP186, and MI-CP197). All clinical studies are being conducted in adult subjects with asthma.

The first clinical study of MEDI-563 in humans was MI-CP158, a Phase 1, open-label, doseescalation study evaluating the safety and tolerability of single IV doses of MEDI-563 (0.003 to 3 mg/kg) in adult subjects with mild asthma. This study has completed enrollment and data analysis is ongoing. A total of 44 subjects have received a single IV dose of MEDI-563 in this study. MEDI-563 was well tolerated in this study. The majority (>85%) of adverse events (AEs) were mild in severity, and there were no deaths, serious adverse events (SAEs), severe AEs, nor any AEs that resulted in MEDI-563 discontinuation. The most common AE was decreased white blood cell count. This finding is consistent with the mechanism of MEDI-563 (ie, depletion of eosinophils in peripheral blood). Another common AE was mild elevations in blood creatine phosphokinase (CPK). A single IV dose of MEDI-563, as low as 0.03 mg/kg, depleted eosinophils in peripheral blood to below the level of detection for at least 8 weeks. In the highdose groups (1.0 and 3.0 mg/kg), the eosinopenia in peripheral blood lasted up to 12 to 16 weeks, respectively. Conversely, in the low-dose groups (0.003 and 0.0003 mg/kg) eosinopenia in peripheral blood lasted an average of 2 weeks and 1 to 2 days, respectively, demonstrating that the effects of MEDI-563 are dose-dependent.

MI-CP186 is a Phase 2, randomized, double-blind, placebo-controlled study evaluating the effect of two IV dose regimens of MEDI-563 (0.3 and 1.0 mg/kg) on the asthma exacerbation rate (relapse and de novo) in adult subjects who required an urgent healthcare visit for treatment of an acute asthma exacerbation.

MI-CP197 is a Phase 2a, randomized, double-blind, placebo-controlled, dose-escalation study evaluating the safety, tolerability, PK, and immunogenicity (IM) of multiple SC doses of MEDI-

563 (25, 100, and 200 mg) in adult subjects with asthma. All subjects have been treated with no serious safety issues reported.

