3.2.2 Blinding

This is a double-blind study. All protocol-associated MedImmune personnel or designees, including the medical monitor, project manager, the statistician, and the site monitors, will be blinded to treatment assignments. In addition, the subject and the clinical site staff including the investigators, study nurses, coordinators, and the Clinical Trial Material Manager (CTMM) will also be blinded. Drug supply management personnel and a limited number of MedImmune personnel who will analyze airway biopsy results, and PK and PD data, will be unblinded during the conduct of the study. Unblinded MedImmune personnel will not be associated with the clinical conduct of the study and will not reveal the treatment assignment of individual subjects to any clinical personnel involved in the study.

Eosinophil and basophil counts in peripheral blood can be a source of unblinding due to the known effects of MEDI-563. Thus, once subjects are treated, eosinophil and basophil counts (including eosinophilic cationic protein (ECP), eosinophilic derived neurotoxin (EDN), and eosinophil- and basophil-derived proteins and cytokines) will not be communicated to the site personnel who evaluate the subjects clinically, except if the information is required for management of AEs or for long-term follow-up of eosinophil counts after the End of Study/Termination visit (Study Day 84 for Cohort 1 or Study Day 140 for Cohort 2).

Study drug will be supplied to the pharmacy in vials with identical appearances in coded kits. Each kit has a unique number that is printed on all labels within the kit (ie, the outer carton label and the label of each vial within the carton). The clinical site staff will order study drug from the pharmacy using the site's normal ordering procedures. The CTMM will prepare the study drug from one or more of the appropriate vials (determined by the subject's weight for Cohort 1 and randomization assignment for Cohorts 1 and 2). Detailed instructions are in the Clinical Trial Material Manual supplied by MedImmune.

If an investigator feels he/she needs to be unblinded to an individual subject's treatment in order to treat an AE, the investigator should follow the instructions for unblinding contained in the IVRS manual.

In the event the treatment allocation for a subject becomes known to the investigator, the investigator or designated staff must notify MedImmune immediately.

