4.2.2 Study Reporting Period for Serious Adverse Events

For Cohort 1, the reporting period for SAEs is from the time the subject signs the informed consent through Study Day 84 or until eosinophil levels in peripheral blood are at least 100 eosinophils/mm³ OR the peripheral blood eosinophil count has returned to at least 70% of the baseline value, if applicable.

For Cohort 2, the reporting period for SAEs is from the time the subject signs the informed consent through Study Day 140 or until eosinophil levels in peripheral blood are at least 100 eosinophils/mm³ OR the peripheral blood eosinophil count has returned to at least 70% of the baseline value, if applicable.

After the initial SAE report the investigator is required to follow each subject proactively and provide further information on the subject's condition to MedImmune Product Safety.

All SAEs should be followed up to resolution by the investigator, even if this extends beyond the study reporting period. Resolution of a SAE is defined as the return to baseline status or stabilization of the condition with the expectation that it will remain chronic.

At any time after completion of the study, if an investigator or qualified designee becomes aware of a SAE that is suspected by the investigator or qualified designee to be related to study product, the event should be reported to MedImmune Product Safety.

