5 STATISTICAL CONSIDERATIONS

5.1 General Considerations

The analysis of study data is the responsibility of MedImmune or its designee. A comprehensive statistical analysis plan will be developed and approved prior to the database lock.

All data will be provided in data listings sorted by dose cohort, treatment groups (MEDI-563 or placebo), and visit number. Summary data will be presented in tabular format by cohort and treatment group. Categorical data will be summarized by the number and percentage of subjects in each category. Continuous variables will be summarized by descriptive statistics including N, mean, standard deviation, median, and range.

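### The by-arm SAE summary runs to the end of an eosinophil-triggered follow-up that MEDI-563 subjects are likelier to enter, so observation time is likely to differ between arms

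*Protocol*

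**What the plan says.** Protocol Section 5.5 gives AEs and SAEs different windows. AEs are described by organ class, severity and "relationship to study drug through Study Day 84 (Cohort 1) or through Study Day 140 (Cohort 2"), the same day for every arm of a cohort. SAEs are described "through Study Day 140 (Cohort 2), or through the end of long-term follow-up, if applicable". That SAE sentence names only Cohort 2's day. Day 84 for Cohort 1 stands in the Abstract (Assessment of Endpoints) and in Section 4.2.2. The Abstract also lets SAE reporting run to the final visit "or until the long-term follow-up period is complete, if applicable".

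The SAE sentence does not itself mention treatment group. That comes from Section 5.1 ("Summary data will be presented in tabular format by cohort and treatment group", with categorical data given as counts and percentages of subjects) and from the end of the Abstract, which says that all endpoints are summarised by cohort and treatment group.

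Sections 1.5, 3.4 and 3.6 set the trigger for long-term follow-up: a blood eosinophil count at the final visit that is below 100/mm³ or below 70% of baseline. Visits then take place every other month, collect a blood count and SAEs, and have no stated maximum. Section 4.2.2 ends the extended reporting period when the count is at least 100/mm³ "OR the peripheral blood eosinophil count has returned to at least 70% of the baseline value, if applicable".

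On what drives the trigger, Section 1.4 reports that after single IV doses of 1.0 and 3.0 mg/kg "the eosinopenia in peripheral blood lasted up to 12 to 16 weeks", respectively. From 0.03 mg/kg upwards, eosinophils were undetectable for at least 8 weeks.

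**The concern.** The length of SAE observation depends on a marker measured after randomisation, and the drug is designed to suppress that marker. If more MEDI-563 than placebo subjects enter long-term follow-up, the drug arms accumulate extra months in which an SAE can be counted. A crude percentage makes no allowance for that. Safety is a primary objective and placebo is the only concurrent comparator. With so few subjects, one late SAE recorded only because a drug subject was still under observation could colour the safety conclusion. Collecting those SAEs is proper. The fault lies in summarising them by arm over unequal time.

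**Working it through.** **Inputs from the protocol.** The fixed windows are D = 84 days (Cohort 1) and 140 days (Cohort 2). The final visit falls 84 − 0 = 84 days after the last dose in Cohort 1 and 140 − 56 = 84 days after it in Cohort 2, which is 12 weeks in both. Cohort 2 has three arms of 4 (8 on drug, 4 on placebo). Visits in the extension are every other month.

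**Inputs assumed, because the protocol does not give them.** These are the SAE risk by Day 140 (5%, varied below), a constant hazard equal in both arms, the shares entering the extension (f), and its length (E = 61, 122 or 183 days, about 2, 4 or 6 months).

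**Plan's own figures first.** Table 6 gives the chance of at least one event as 1 − (1 − p)ⁿ. At p = 5%, n = 8 gives 1 − 0.95⁸ = 33.7% and n = 4 gives 1 − 0.95⁴ = 18.5%. Both match the table, as do its other entries. Table 6 assumes one risk for everyone and so does not address unequal follow-up.

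**Is differential entry plausible?** The trigger visit is 12 weeks after the last dose. Reported eosinopenia after one IV dose lasted up to 12 weeks at 1.0 mg/kg and up to 16 weeks at 3.0 mg/kg. At the 80 kg example weight in Section 3.3.3, the SC doses are 100/80 = 1.25 and 200/80 = 2.5 mg/kg, each given three times. SC bioavailability is not stated, so this is only a rough comparison. Entry mainly from the drug arms is likely but remains an inference.

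**Effect on crude incidence, Cohort 2.** The hazard is h = −ln(0.95)/140 = 0.000366 per day. An arm's incidence is

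1 − [(1 − f)·exp(−hD) + f·exp(−h(D + E))].

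- An extended subject with E = 61 has risk 1 − 0.95^(201/140) = 7.10%, against 5.00% for a subject who is not extended.
- All drug, no placebo extended: 7.10/5.00 = 1.42.
- 75% of drug, 25% of placebo extended: drug 0.75 × 7.10 + 0.25 × 5.00 = 6.57%; placebo 0.25 × 7.10 + 0.75 × 5.00 = 5.52%; ratio 1.19.

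| Share entering (drug / placebo) | 2 months | 4 months | 6 months |
|---|---|---|---|
| 100% / 0% | 1.42 | 1.83 | 2.23 |
| 50% / 0% | 1.21 | 1.42 | 1.62 |
| 75% / 25% | 1.19 | 1.34 | 1.47 |
| 50% / 50% | 1.00 | 1.00 | 1.00 |

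The ratio hardly depends on the assumed risk. For 100% / 0% and two months it is 1.43, 1.42 and 1.40 at risks of 2.5%, 5% and 10%.

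**Effect on one Cohort 2 dose arm (n = 4), one 60-day interval, all four extended.** At 5% risk, the chance of at least one SAE goes from 18.5% to 1 − 0.95^(4 × 200/140) = 25.4%. At 1% risk it goes from 1 − 0.99⁴ = 3.9% to 1 − 0.99^(4 × 200/140) = 5.6%.

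**With a common cut-off at Day 140,** both arms have 5.0% and the ratio is 1.00 whatever the entry pattern. SAEs per unit of person-time also give 1.00 under equal constant hazards.

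**The case against.** The strongest reply is that little rides on this. The safety analysis is descriptive, the sample size rests on clinical judgment, and Section 5.1 requires listings by cohort, treatment group and visit, so an SAE after Day 140 can be picked out. A statistical analysis plan is promised before database lock and could split the periods. Section 1.4 reports no SAEs in the 44 subjects dosed in the first-in-human study and none in the 13 Cohort 1 subjects. All of that stands, and it limits the size of the problem. It does not undo the window that Section 5.5 states, which already differs from the AE window beside it.

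A reader might go further in four ways that the protocol does not support.

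- *That MEDI-563 subjects will be kept under observation and placebo subjects will not.* No entry rates are given. The 12 weeks at 1.0 mg/kg is an upper duration that ends at the trigger visit, no duration is given for the SC regimens, and a placebo subject below 70% of baseline also meets the entry wording.
- *That late SAEs are judged unblinded.* Section 3.2.2 withholds eosinophil counts from sites "except if the information is required for management of AEs or for long-term follow-up of eosinophil counts after the End of Study/Termination visit". This releases counts, not treatment codes, and Section 5.2 keeps sites blinded to assignment until the last subject completes and the database is locked. Since Section 3.2.2 itself says that counts can unblind, the risk is real, but it is only a risk.
- *That starting AE reporting at consent biases the comparison.* Events before randomisation cannot systematically favour an arm, and the Abstract and Section 4.1.2 define only a reporting period.
- *That drug risk and extra observation time cannot be separated at all.* The listings allow it; the by-arm percentage does not.

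**Conclusion.** The point holds as a modest defect in the current text. Section 5.5, read with Section 5.1 and the Abstract, gives a crude by-arm SAE percentage over a period that is likely to be longer on drug. Under equal hazards this pushes the drug figure up. Any plausible pattern with more entry on drug gives a ratio above 1, and the bias disappears if entry is similar in both arms.

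The size is illustrative. For a two-month extension in Cohort 2 the ratio is about 1.2 to 1.4 under the unequal entry patterns shown, and longer extensions give more. These figures rest on an assumed SAE risk, assumed entry shares, an assumed extension length and a constant hazard. The protocol supplies none of these.

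Bigger numbers can be produced for Cohort 1, because 61 extra days weigh more against 84 than against 140. A reader should not lead with them: that cohort has completed the study with no SAEs. The practical exposure is the reading of one or two events, mostly in Cohort 2.

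**What to change.** In Section 5.5, end the by-arm SAE summary at Day 84 (Cohort 1) and Day 140 (Cohort 2) for every arm, as is already done for AEs, and name both days. Leave SAE collection in long-term follow-up as it is, including the reporting period in the Abstract and Section 4.2.2. Present SAEs after those days in a separate listing with each subject's follow-up time. If the whole period is to be summarised by arm, give SAEs per unit of person-time. Note on the listing that sites may have seen eosinophil counts when judging relationship to study drug.

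The entry and exit wording for long-term follow-up should also be reconciled, because it determines who is observed longer. As written, a subject at or above 100/mm³ but below 70% of baseline meets the entry wording and the exit wording at once.

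The cost is a few words and one listing, and no data are lost. The small downside is that late SAEs leave the main by-arm table, so the study report must point readers to the listing.

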5.6 Secondary Endpoints

The secondary objectives of this study are to evaluate the PK and IM of MEDI-563. Plasma MEDI-563 concentration data will be tabulated by cohort together with descriptive statistics. Individual and mean plasma concentration-time profiles of MEDI-563 by dose cohort will be generated. Noncompartmental PK data analysis of plasma concentrations of MEDI-563 will be performed using the software package WinNonlin®. The noncompartmental pharmacokinetic parameters to be obtained and reported include, but are not limited to: the C_{max}, AUC, terminal elimination half-life ($t_{1/2}$) and systemic clearance (CL) if the data allows. For Cohort 2 subjects, C_{max} and pre-dose trough (C_{min}) plasma concentrations will be summarized following each dose. Descriptive statistics of these noncompartmental parameters by dose cohort will also be provided. Immunogenicity results will be listed for all subjects and the percentage of subjects who developed detectable anti-MEDI-563 antibodies will be calculated and reported.

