Skin Prick Test	Х											
Assess eNO ^b		Х				Х			Х		Х	
Spirometry at Site	X	Х	Χ	Χ	Х	Х	Х	Х	Х	X	Х	
Collect Subject Home Peak Flow Monitoring, Use of Rescue \(\beta\) 2 Agonists		Х	X	X	X	Х	X	X	Х	Х	Х	

MEDI-563											Protocol	#MI-CP166
MedImmune											; Final `	Version 7.0
			1			1			1	1	1	
Study Day											140	Long-term
	Screening	0	1	7	21	28	56	77	84	119	(End of Study /	Follow-up ^e
	(-14 D to -1 D)										Study Termination)	-
Visit		1	2	3	4	5	6	7	8	9	10	
Asthma Control Questionnaire (ACQ)		Х		Х		Х	Х		Х	Х	Х	
AQLQ(S)		Х				Х	Х		Х		Х	
CORRELATIVE STUDIES												
Bronchoscopy with Airway Mucosal Biopsies	X °								Х			
Sputum Induction and Collection	Х					Х		Х		Х	Х	
Bone Marrow Aspiration ^d	Х								Х			
Serum for Eosinophil- and Basophil-derived		v	v	v		v	v		v		v	
Proteins, Cytokines		Λ	л	Λ		Λ	Λ		Λ		Λ	
Whole blood for WBC counts (flow cytometry) ^f		Х	Х	Х		Х	Х		Х		Х	
Serum and Whole Blood for RNA for Storage		Х		Х		Х	Х		Х		Х	
DNA Sample		Х										
PK/IM												
MEDI-563 Plasma Concentration		Х	Х	Х	Х	Х	Х		Х	Х	Х	

Page 32 of 91

Table 5 Footnotes:

Anti-MEDI-563 Antibodies

.

a For women of childbearing potential, unless surgically sterile or 1 year postmenopausal. Serum BHCG at screening and urine BHCG on Study Days 0, 28, and 56 must be negative prior to administration of the study drug.

Х

Х

Х

- b Exhaled nitric oxide (eNO) must occur before spirometry.
- c Bronchoscopy with airway mucosal biopsies needs to be completed at least 7 days after the screening sputum induction, and within 2 days prior to Study Day 0 (study drug administration).

Х

- d Bone marrow aspiration is optional.
- e If at the End of Study/Study Termination Visit (Study Day 140) eosinophil levels in peripheral blood are not at least 100 eosinophils/mm³ OR the peripheral blood eosinophil count has not returned to at least 70% of the baseline value, subjects will return to the study site every other month for additional evaluations.
- f Two separate samples will be drawn.
- g SAEs only.

3.4.1 Study Procedures for Cohort 1

All subjects in Cohort 1 will receive study drug on Study Day 0 only.

Screening

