 - CBC with differential
- 2. Assess for SAEs

3.4.2 Study Procedures for Cohort 2

Subjects in Cohort 2 will receive study drug on Days 0, 28, and 56.

Screening

All screening laboratory assessments must be performed within 14 days before Study Day 0. The screening evaluations may be carried out over more than 1 visit. Written informed consent must be obtained prior to performing any study-related procedure, including screening evaluations. Screening laboratory test results must be reviewed by the investigator or qualified designee, prior to Study Day 0. Clinically significant abnormal results on screening laboratory tests may be repeated once at the discretion of the site investigator(s) or qualified designee. If a CXR was performed within 6 months prior to screening or if a positive skin prick test was obtained, they need not be repeated if results are obtainable and the subject consents to allow their use.

The following evaluations must be completed within 14 days prior to Study Day 0:

- 1. Written informed consent
- 2. Verify eligibility criteria
- 3. Screening medical history, including history of tobacco use and comprehensive asthma history
- 4. Screening physical examination, including body height and weight
- 5. Assess AEs and SAEs
- 6. Review and record concomitant medications
- 7. Vital signs, including temperature, blood pressure, pulse rate, and respiratory rate
- 8. 12-lead ECG
- 9. Urinalysis

10. CXR (may be omitted if subject has documentation of previous x-ray in last 6 months)

- 11. Mantoux (PPD) test
- 12. Skin prick test (may be omitted if subject has documentation of a previous skin prick test)
- 13. Spirometry at site
- 14. Sputum induction and collection to evaluate eosinophil counts
- 15. Blood collection for screening
 - Screening chemistry panel (see Section 3.5.5 for details)
 - CBC with differential
 - Prothrombin time (PT)/Partial thromboplastin time (PTT)
 - Serum for hepatitis A antibody, hepatitis B surface antigen, hepatitis C antibody and HIV-1 and HIV-2 antibody
 - Serum βHCG (for women of childbearing potential and are not surgically sterile or at least 1 year post-menopausal)
- 16. Provide subjects with electronic home peak flow meter to collect peak flow results at home and use of rescue $\beta 2$ agonists.

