Results from all the tests listed above should be obtained and reviewed prior to the bronchoscopy or bone marrow aspiration. The following tests should only be completed after all other study eligibility criteria are met.

- 1. Bone marrow aspirates (optional test that requires signing a separate informed consent form)
- 2. Bronchoscopy with airway mucosal biopsies

The bronchoscopy with airway mucosal biopsies needs to be completed at least 7 days after the sputum induction, and within 2 days of Study Day 0 (study drug administration).

Study Day 0: Study Drug Administration (Visit 1)

The following procedures will be completed prior to study drug administration:

- 1. ACQ
- 2. AQLQ(S)
- 3. Verify eligibility criteria
- 4. Update screening medical and asthma history and physical examination (any new findings since screening)
- 5. eNO (prior to spirometry)
- 6. Spirometry at site
- 7. Assess AEs or SAEs since last visit
- 8. Record concomitant medications
- 9. Vital signs (temperature, blood pressure, pulse rate, respiratory rate) prior to administration of study drug
- 10. Baseline blood collection prior to study drug administration for:
 - Serum chemistry
 - CBC with differential
 - Serum CRP, ECP, EDN, IL-5, and IL-6
 - Serum tryptase

- MEDI-563 plasma concentration
- Whole blood for WBC counts (flow cytometry) 2 separate samples must be collected
- Serum and whole blood for RNA for storage
- Anti-MEDI-563 antibodies
- Serum for eosinophil- and basophil-derived proteins, cytokines
- DNA sample (optional test that requires signing a separate informed consent form)

11. Urinalysis

- 12. Urine βHCG (for women of childbearing potential and are not surgically sterile or at least 1 year post-menopausal) must have negative result prior to study drug administration
- 13. Collect subject's daily home peak flow results and rescue $\beta 2$ agonist use
- 14. Randomization and assignment of PID.

Study Drug Administration

- 1. Administer Study Drug
- 2. Vital signs (including temperature, blood pressure, pulse rate, and respiratory rate) will be taken as follows:
 - Immediately after study drug administration (+ 5 minutes)
 - Every 30 minutes (± 5 minutes) for 2 hours after study drug administration or until stable, whichever is later
- 3. Assess injection sites
- 4. Blood draw for MEDI-563 concentration and serum CRP, ECP, and IL-6 analysis **2 hours** after completion of study drug administration.

Study Day 1 (+ 1 day): (Visit 2)

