 - Serum CRP, ECP, EDN, IL-5, and IL-6
 - Serum tryptase
 - Whole blood for WBC counts (flow cytometry) 2 separate samples must be collected
 - Serum and whole blood for RNA for storage
 - MEDI-563 plasma concentration
 - Anti-MEDI-563 antibodies
- 9. Urinalysis
- 10. Urine BHCG (for women of childbearing potential and are not surgically sterile or at least 1 year post-menopausal) negative result must be obtained prior to study drug administration
- 11. eNO (prior to spirometry)
- 12. Spirometry at site
- 13. Sputum induction and collection
- 14. Collect subject's daily home peak flow results and rescue $\beta 2$ agonist use.

Study Drug Administration

- 1. Administer Study Drug
- 2. Vital signs (including temperature, blood pressure, pulse rate, and respiratory rate) will be taken as follows:
 - Immediately after study drug administration (+ 5 minutes)
 - Every 30 minutes (± 5 minutes) for 2 hours after study drug administration or until stable, whichever is later
- 3. Assess injection sites
- 4. Blood draw for serum CRP, ECP, and IL-6 analysis **2 hours** after completion of study drug administration.

Study Day 56 (± 3): Study Drug Administration (Visit 6)

The following procedures will be completed prior to administration of study drug:

- 1. ACQ
- 2. AQLQ(S)
- 3. Record any changes to concomitant medications
- 4. Vital signs (temperature, blood pressure, pulse rate, and respiratory rate) prior to study drug administration
- 5. Physical examination
- 6. Assess AEs and SAEs

- 7. Assess injection sites
- 8. Blood collection for:
 - Serum chemistry
 - CBC with differential
 - Serum for eosinophil and basophil derived proteins, cytokines
 - Serum CRP, ECP, EDN, IL-5, and IL-6
 - Whole blood for WBC counts (flow cytometry) 2 separate samples must be collected
 - Serum and whole blood for RNA for storage
 - MEDI-563 plasma concentration
- 9. Urinalysis
- 10. Urine BHCG (for women of childbearing potential and are not surgically sterile or at least 1 year post-menopausal) negative result must be obtained prior to study drug administration
- 11. Spirometry at site
- 12. Collect subject's daily home peak flow results and rescue $\beta 2$ agonist use

Study Drug Administration

- 1. Administer Study Drug
- 2. Vital signs (including temperature, blood pressure, pulse rate, and respiratory rate) will be taken as follows:
 - Immediately after study drug administration (+ 5 minutes)

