3.5.9 Pharmacokinetic Evaluations

Plasma will be collected for MEDI-563 concentration determination. The study schedule outlines when these samples will be collected. On study drug administration days (ie, Day 0 for Cohort 1 and Days 0, 28, and 56 for Cohort 2), blood samples will be drawn as follows:

Cohort 1

• Day 0: Just prior to study drug administration and 2 hours after study drug administration.

Cohort 2

- Day 0: Just prior to study drug administration and 2 hours after study drug administration
- Day 28: Just prior to study drug administration only
- Day 56: Just prior to study drug administration only

The requirements for sample collection, preparation, storage, and shipping are specified in the laboratory manual provided to the sites.

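### Cohort 2 Cmax is promised after every dose, but no plasma sample is scheduled near the expected peak after doses 2 and 3

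*Protocol*

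**What the plan says.** Section 5.6 of the Protocol, repeated in the abstract under the assessment of endpoints, commits to Cohort 2 Cmax and Cmin that "plasma concentrations will be summarized following each dose". Section 3.4.2 sets three doses: "Subjects in Cohort 2 will receive study drug on Days 0, 28, and 56".

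Section 3.5.9 then fixes the dosing-day samples for Cohort 2. The first dose gets two draws, one on each side of the injection: "Day 0: Just prior to study drug administration and 2 hours after study drug administration". The second dose gets a single draw, and the entry rules out any later one that day: "Day 28: Just prior to study drug administration only". The third dose is handled in the same way as the second: "Day 56: Just prior to study drug administration only".

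The row "MEDI-563 Plasma Concentration" in Table 5 is marked at Days 0, 1, 7, 21, 28, 56, 84, 119 and 140, and not at Day 77.

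The Section 3.4.2 visit lists agree. The 2-hour post-dose item on Day 0 reads "Blood draw for MEDI-563 concentration and serum CRP, ECP, and IL-6 analysis". On Days 28 and 56 the corresponding item is only "Blood draw for serum CRP, ECP, and IL-6 analysis", without drug concentration. The Day 77 list has no blood draw.

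**The concern.** Cmax for a dose can be read only from samples that bracket its peak. The protocol fixes such samples for the first dose and none for the other two, yet promises the parameter for all three without a condition. If the promise is carried out literally, the largest value available after doses 2 and 3 is a concentration from about the end of the dosing interval. Set beside a genuine early-interval maximum after dose 1, it would suggest that peak exposure drops on repeat dosing.

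PK is one of the two secondary objectives, and Cohort 2 is the only multiple-dose SC cohort in this study, so its table by dose is where a reader would look for the effect of repeat dosing on exposure.

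**Working it through.** **Step 1. Time since the latest dose, nominal days (Table 5, Sections 3.4.2 and 3.5.9).**

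| Dose | Day given | Samples up to the end of the 28-day interval |
|---|---|---|
| 1 | 0 | 2 h, 1 d, 7 d, 21 d, 28 d (pre-dose 2) |
| 2 | 28 | 28 d (Day 56, pre-dose 3) |
| 3 | 56 | 28 d (Day 84) |

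Dose 1 has four samples before the end of its interval; doses 2 and 3 have none. For dose 2 the maximum and the trough are one and the same sample. For dose 3 the later samples are at 119 − 56 = 63 and 140 − 56 = 84 days, so the Day 84 value is the one expected to be reported as the maximum.

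**Step 2. Visit windows (Section 3.4.2: ±3 days at Days 28 and 56, +7 at Day 84).**
- After dose 2: from (56 − 3) − (28 + 3) = 22 to (56 + 3) − (28 − 3) = 34 days.
- After dose 3: from 84 − (56 + 3) = 25 to (84 + 7) − (56 − 3) = 38 days.

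**Step 3. Illustrative size.** Section 1.5 anticipates that 12 weeks exceeds 5 half-lives, which implies a half-life below 84/5 = 16.8 days. The protocol gives no time of peak for the SC route; 3 to 7 days is an assumption. With mono-exponential decline, the fraction of the peak left g days after dosing is 2^(−(g − tmax)/t½).

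| Half-life | g | Peak at day 3 | Peak at day 7 |
|---|---|---|---|
| 16.8 d | 28 d (nominal) | 2^(−25/16.8) = 0.36 | 2^(−21/16.8) = 0.42 |
| 16.8 d | 22 d (shortest after dose 2) | 2^(−19/16.8) = 0.46 | 2^(−15/16.8) = 0.54 |
| 16.8 d | 25 d (shortest after dose 3) | 2^(−22/16.8) = 0.40 | 2^(−18/16.8) = 0.48 |
| 10 d (assumed) | 28 d (nominal) | 2^(−25/10) = 0.18 | 2^(−21/10) = 0.23 |

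**Step 4. Direction, allowing for carry-over.** Under the same assumptions with a 16.8-day half-life, the true dose-2 peak is 1 + 2^(−28/16.8) = 1.31 times the dose-1 peak. The Day 56 value is 0.36 × 1.31 = 0.47 to 0.42 × 1.31 = 0.55 of the dose-1 peak. At the 22-day extreme (dose 2 on Day 31, sample on Day 53) it reaches at most 0.54 × (1 + 2^(−31/16.8)) = 0.54 × 1.28 = 0.69. The true peak rises while the reported one falls.

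**The case against.** **A data-permitting caveat exists.** In Section 5.6 it closes the general parameter list that precedes the Cohort 2 sentence; the abstract ties it to Cohort 1. The Cohort 2 sentence carries no caveat in either place. It softens the general list but does not cover this promise.

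**Readers would see the sampling times.** Section 5.6 also plans concentration tables and individual and mean profiles. That is fair: a careful reader could notice that the only values after doses 2 and 3 lie about 28 days out. It lowers the chance of being misled but does not make the promised parameter estimable.

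**The stakes are modest.** This stands. Each active arm has about 4 subjects, the summaries are descriptive, and no primary endpoint or in-study dose decision uses this parameter. Section 1.4 also describes a separate study that evaluates PK after multiple SC doses including 100 and 200 mg.

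**The timing is not rigid.** This also stands. Besides the windows, Section 3.3.4.2 allows a delayed injection of up to 7 days for acute illness, which could shorten a gap further, and an early-discontinuation visit could add a stray sample. Neither is a scheduled sample near the peak.

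**Stronger readings that the documents do not support.** A reader might infer that a planned accumulation ratio will be wrong; the protocol plans no such ratio. A reader might also take 36% to 42% as an upper limit. It is not: it holds only at nominal timing under simple exponential decline, and the half-life limit comes from an anticipated figure, not a measured one.

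**Conclusion.** The inconsistency holds within current text: Section 5.6 and the abstract promise a parameter that Section 3.5.9, Table 5 and the visit lists do not allow for two of the three doses. This conclusion needs no assumption about the drug; it follows from the sampling days alone.

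The size is illustrative. It rests on the half-life limit, the assumed 3-to-7-day peak and mono-exponential decline set out above. On these, the reported value is roughly a third to a half of the true peak, and less with a shorter half-life.

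Severity is should-fix, not must-fix: safety, the biopsy endpoint and the conduct of the trial are unaffected. Dose-1 Cmax can be estimated, but only coarsely, since nothing is sampled between Day 1 and Day 7 or between Day 7 and Day 21.

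**What to change.** Reconcile Section 5.6 and the abstract with Section 3.5.9 and Table 5:
- Limit Cohort 2 Cmax to the first dose, and state that samples at 2 h and Days 1, 7 and 21 resolve the peak only coarsely.
- Report the Day 28 and Day 56 pre-dose troughs and the Day 84 concentration as the end-of-interval values for doses 1, 2 and 3. Label Day 84 as end-of-interval, because no fourth dose follows.
- Base any comparison of exposure across doses on these end-of-interval concentrations, with actual times since dose listed.

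The cost is a wording change in two places, with no added samples or visits. The sponsor gives up only a parameter that the schedule cannot supply. If Cmax after doses 2 and 3 is wanted, the other route is to add post-dose samples after those doses, at the price of extra draws and visits.
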